The primary objective of this proposal is to add to the palette of treatment options by comparing the effect of two opioid dependence treatment delivery models on improving the HIV care engagement and outcomes in Vietnam. We propose a multisite, open-label, randomized, flexible-dose noninferiority trial of buprenorphine/naloxone (BUP/NX) (n=225) versus methadone maintenance therapy (MMT) referral (n=225) for treatment of opioid dependence in HIV-infected participants in 6 Vietnam HIV clinic research sites. The study is conducted in partnership with colleagues at Hanoi Medical University (HMU), the Provincial AIDS Control (PAC) authorities of Hanoi, Thanh Hoa, and Bac Giang, the Vietnam National Institute of Mental Health, and Oregon Health & Science University.

Study sites are 4 HIV clinics in Hanoi, 1 in Thanh Hoa, and 1 in Bac Giang; epicenters of Vietnam's HIV and heroin epidemics, all of which are associated with MMT and HIV testing and counseling centers. A research coordinating center at HMU provides additional outreach, recruitment, non-medication-related study procedures and links participants to participating HIV clinic sites for clinical management. HIV providers will be trained to manage opioid dependence using BUP/NX.

Participants are HIV-infected participants with opioid dependence new to HIV care, recruited from HIV clinics, MMTs, and associated HIV testing centers. Participants randomized to BUP/NX will receive BUP/NX after successful completion of medication induction and stabilization. Participants randomized to BUP/NX will receive a taper after 12 months of study drug exposure, with referral for MMT. Participants randomized to MMT will receive usual care, which is case-manager-assisted referral to MMT. All participants receive clinic-based individual counseling and HIV care.

The primary outcome of HIV-1 viral load will be measured at baseline, 6, and 12 months. Secondary outcomes, including self-reported drug use, urine drug screens (UDS), and measures of HIV care engagement (adherence, retention) will be assessed quarterly through 12 months follow-up. Qualitative interviews with participants, family members of participants, and providers in years 1 through 4 will identify lessons-learned for scale-up of HIV clinic-based BUP/NX.

Figure 2. Study Schema

There are three specific aims in this protocol:

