Substance use disorders impair participant engagement and retention in HIV care, contributing to gaps in the HIV care cascade.^{3,34} The current study seeks to compare clinic-based BUP/NX versus referral for MMT for treating opioid dependence in HIV-infected participants to improve engagement and retention in HIV treatment that leads to HIV viral suppression (Figure 2). Virologic suppression reduces HIV associated morbidity, prolongs survival, restores and preserves immunologic function and decreases HIV transmission³⁵. As shown in the conceptual model below, decreased use of opioids (Aim 2) and uptake of and adherence to ART (Aim 1B) are proximal outcomes that contribute to virologic suppression (Aim 1A). HIV-infected Injection Drug Users (IDU) who initiate ART should be able to achieve virologic suppression within 6-12 months if they continue in HIV care and adhere to ART.³⁶⁻³⁸ In this model, successful treatment of opioid dependence is hypothesized as an important moderator of HIV care engagement and subsequent viral suppression. HIV-infected IDU who receive treatment for substance use are more likely to use HIV care and receive ART.³⁹⁻⁴¹ Participant and provider attitudes toward treatment and organizational characteristics, assessed in Aim 3, influence adoption of new treatment modalities and provide lessons learned for wide-scale implementation.⁴² The Consolidated Framework for Implementation Research (CFIR)⁴³⁻⁴⁴ suggests that participant, provider, and organizational factors are key inputs to adoption of new evidence-based technologies in healthcare (Aim 3).

Figure 3. Conceptual Model

Setting

Hanoi, Thanh Hoa, and Bac Giang are epicenters of the Vietnam HIV epidemic with high numbers of HIV-infected heroin users. Care innovations in these provinces often serve as models for others to follow. Six outpatient HIV clinics (OPC) will participate in the clinical trial as clinical research sites: 4 clinics in Hanoi (Tu Liem, Long Bien, Hoang Mai and Dong Da), 1 clinic in Thanh Hoa (Thanh Hoa PAC OPC), and 1 clinic in Bac Giang (Bac Giang PAC OPC). A

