Participants are randomized to clinic-based BUP/NX vs. referral for MMT. This is a non-blinded study. Randomization will be conducted by computer generated random number sequence in blocks of 10 prepared by statisticians at OHSU. Allocation assignments will be maintained in sealed, sequentially numbered envelopes by the Vietnam Research Coordinating Center (RCC) at Hanoi Medical University. HIV clinic site research assistants will call the RCC to receive allocation assignment when a participant is deemed eligible for study participation.

Pilot Data Collection and Assessments

The data collection instruments were pilot-tested with participants at four additional sites: Bac Giang PAC OPC; Bac Giang Provincial Hospital OPC; Viet Tri, Phu Tho PAC OPC; and Phu Tho Town Community Health Center OPC.

Table 2: Table of Assessments								
	Pre-Screening	Screening	Baseline	3 Month	6 Month	9 Month	12 Month	As Needed Only
Visit Window	--	60 days after Pre-Screening		+/- 14 days	+/- 14 days	+/- 14 days	-14 days/+30 days	--
Pre-Screening Consent Form	X							
Informed Consent		X						
Informed Consent Quiz		X						
Progress Note		X	X	X	X	X	X	X
Visit Checklist	X	X	X	X	X	X	X	
Locator Form	X	X	X	X	X	X	X	
Master Enrollment Log	X	X	X					
Communication Log								X
Compensation 
 • Log • Receipt 		X	X	X	X	X	X	
Data Collection Forms								
Inclusion/Exclusion Criteria (Eligibility Checklist)			X					
Pre-Screening Survey	X							
Screening Survey		X						
Baseline Survey			X					
3 Month Survey				X				
6 Month Survey					X			
9 Month Survey						X		
12 Month Survey							X	
ASI-lite Table			X	X	X	X	X	
Randomization Form			X					
Physical Exam			X					
Dosing Form 
 • BUP/NX • MMT 				X	X	X	X	
HIV Care Utilization Form				X	X	X	X	
Fatal Overdose Form								X

Table 2: Table of Assessments								
	Pre-Screening	Screening	Baseline	3 Month	6 Month	9 Month	12 Month	As Needed Only
Pregnancy and Birth Control Assessment • Includes Urine Test		X	X	X	X	X	X	
Confirmed Pregnancy Test								X
Early End of BUP/NX								X
HIV Viral Load			X		X		X	
CD4*		X*			X*		X*	
HIV genotype resistance testing (as necessary)			X				X	
HIV confirmatory testing (as necessary)		X						
HIV rapid testing	X							
Tuberculosis (PPD Skin Test)*			X*					
Hepatitis B/C*			X*					
Safety Labs* • CBC • AST/ALT •		X*						
UDS • Morphine • Methadone • Methamphetamine • Amphetamine • Buprenorphine	X	X		X	X	X	X	

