The primary analysis for this study will be a mixed logistic regression model comparing BUP/NX versus MMT on viral suppression rates over time. Treatment comparisons will be performed under the Intent-to-Treat (ITT) criterion; participants will be analyzed in the arm to which they

were randomized regardless of subsequent events. In this mixed logistic model, each (binary) outcome serves as a dependent variable; treatment effect (BUP/NX versus MMT referral) and time effect (e.g., baseline, 6, and 12 months) will be considered main effects. An interaction between these two main effects, e.g., treatment*time, will be included in the model. Model-fitted, marginal risk and RD estimates will be obtained at each time by applying an inverse-logit transformation to coefficients from the logistic regression model, with standard errors estimated via the delta method. We will test the primary hypothesis of noninferiority by comparing the lower bound of a 95% confidence interval to the prespecified margin (i.e., 13%); if the lower confidence limit of the RD is greater than -13%, we will conclude that the BUP/NX is noninferior to MMT. The model will include subject-level random intercepts in order to account for repeated measurements within individuals. Attrition is unavoidable in a longitudinal study; in our study, we anticipate an attrition rate of 20%. The mixed model approach is a recommended strategy for handling missing data in clinical trials under the assumption that the data are missing at random.

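### The primary and Aim 2 models have no clinic term, and the plan does not say whether allocation was stratified by clinic: a modest loss of precision, not a bias

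*Combined protocol and SAP*

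**What the plan says.** All references are to the combined protocol and SAP.

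- **Primary model (Data Analysis, Aim 1, Data Analysis Plan).** Treatment is one main effect; the "time effect (e.g., baseline, 6, and 12 months) will be considered main effects" as well. "An interaction between these two main effects, e.g., treatment*time, will be included in the model". The only random effect is for the participant: "The model will include subject-level random intercepts in order to account for repeated measurements within individuals". The 12-month RD comes from an inverse-logit transformation of the coefficients with a delta-method standard error, and noninferiority is declared if the lower 95% limit lies above -13%.
- **Covariates and sensitivity analyses (Aim 1).** The covariates that may be considered are all participant characteristics; clinic is not among them. None of the three sensitivity analyses uses clinic.
- **Aim 2, Data Analysis Plan.** It adopts the Aim 1 approach, so the same gap carries over.
- **Randomization.** Allocation is by "computer generated random number sequence in blocks of 10", held centrally at the coordinating centre. No stratification factor is named, and nothing says that there was none.
- **Objectives, Setting, and Study sites and dosing sites.** "Six outpatient HIV clinics (OPC) will participate in the clinical trial as clinical research sites": four in Hanoi and one each in Thanh Hoa and Bac Giang. Two of the Hanoi clinics provide only clinical management and dispensing; coordinating-centre staff carry out the other study procedures for them.

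**The concern.** Clinic plausibly predicts 12-month suppression in both arms. Each clinic's own providers deliver HIV care and BUP/NX, its own case managers arrange the methadone referral, and the affiliated methadone programmes are local. The protocol's conceptual model treats organisational characteristics as influencing adoption, and Aim 3 sets out to compare sites.

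A baseline factor that predicts the outcome but is left out of the model leaves its variance in the comparison. If one list serves all six clinics, blocks of 10 balance the overall totals but not the arms within each clinic. If the list was in fact issued by clinic, the design has removed that variance but the model's standard error does not reflect it. Either way, the interval whose lower limit decides noninferiority is wider than it needs to be. What is at stake is power. The plan states none for the noninferiority comparison, and on its own inputs power is below 80%.

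**Working it through.** **1. The plan's own figure.** The Power Analysis for the superiority design gives 170 per arm for 50% versus 65%, 80% power and alpha .05. With pooled variance under the null and two-sided alpha:

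n = [1.96 × √(2 × 0.575 × 0.425) + 0.8416 × √(0.5 × 0.5 + 0.65 × 0.35)]² / 0.15² = (1.370 + 0.582)² / 0.0225 ≈ 169.3, rounded up to 170.

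It reproduces, and the clinic question does not affect it.

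**2. Inputs for the noninferiority check.**
- From the documents: 225 per arm; 20% attrition, so 225 × 0.8 = 180 evaluable per arm; 50% suppression under MMT referral; margin 13 points; two-sided 95% interval.
- Assumed: the same 50% in the BUP/NX arm (true RD 0), and a between-clinic SD s of 5, 10 or 15 points. The documents give no value for s.

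**3. Formulas.**
- Unadjusted: SE = √(2 × p(1-p) / n) = √(2 × 0.25 / 180) = 5.27 points.
- Clinic-adjusted: SE = √(2 × [p(1-p) - s²] / n).
- Power = Φ(0.13 / SE - 1.96).
- Share of outcome variance explained by clinic = s² / 0.25.
- SD of the chance clinic-imbalance part of the RD = 2s / √360.

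| s (points) | Variance explained | SE (points) | Power, 180/arm | Power, 225/arm | Imbalance SD (points) |
|---|---|---|---|---|---|
| No clinic term | – | 5.27 | 69.4% | 78.7% | – |
| 5 | 1% | 5.24 | 69.8% | 79.2% | 0.5 |
| 10 | 4% | 5.16 | 71.1% | 80.4% | 1.1 |
| 15 | 9% | 5.03 | 73.4% | 82.4% | 1.6 |

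The corresponding gain in effective sample size is 450 × [1/(1 - share) - 1], or about 5, 19 or 45 participants.

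**4. The imbalance SD is not an extra effect.** At s = 10, the unadjusted variance is 5.27² = 27.8 and the adjusted variance 5.16² = 26.7 (squared points). The difference of 1.1 equals the imbalance variance, 1.054² = 1.1. With unstratified allocation the wider interval already covers the chance imbalance.

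**5. Other suppression rates (180 per arm, equal arms).** At 65%, power goes from 73.4% to 73.9%, 75.3% or 77.8%. At 80%, it goes from 86.9% to 87.4%, 89.0% or 91.4%.

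**6. Simulation.** 6,000 trials per setting, 360 evaluable, six equal clinics, blocks of 10, 12-month RD from a linear model with robust SE. This simplifies the planned mixed logistic model.
- Bias of the unadjusted RD: at most 0.1 point in every setting.
- One-sided error at a true RD of -13 points, unstratified blocks, no clinic term: 2.0% to 2.6%, against 2.5% nominal.
- Power with unstratified blocks: 68.4% to 70.3% at s = 10, and 68.5% to 73.0% at s = 15, when clinic is added.
- Clinic-stratified blocks, clinic omitted, s = 15, true RD of -13 points: actual SD 4.95 against mean SE 5.18 points; error 1.8%, so conservative.
- No clinic differences (s = 0), unstratified blocks: mean SE rises from 5.27 to 5.31 points (0.04 / 5.27 = 0.8%) when clinic is added, with no visible loss of power.

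**The case against.** The strongest reply is that nothing here is invalid. Randomisation is individual, the unadjusted RD is unbiased, and the false-claim rate is at or below nominal. That stands. A reader might infer that omitting clinic biases the noninferiority estimate or makes a false claim of noninferiority more likely; the simulation shows neither.

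Second, the benefit is small and rests on an assumed SD. That also stands. With normally distributed clinic effects, an SD of 15 points across six clinics implies an expected best-to-worst gap of about 2.5 × 15 = 38 points, which is extreme. Common clinic selection criteria and one central viral load laboratory argue for smaller differences. At an SD of 5 points the gain is 0.4 points of power.

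Third, a reader might count chance clinic imbalance as a harm on top of the wider interval. Step 4 of the working shows that they are the same variance.

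Fourth, silence on stratification is not evidence that there was none. The documents support a request to state what was done, not a finding that allocation was unstratified.

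Fifth, adjustment is not entirely free. With clinic indicators in a logistic model, the planned inverse-logit of coefficients would depend on which clinic is the reference, so the RD step needs rewriting. Clinic also needs a definition: the coordinating centre links participants to clinics, the documents do not say when, and two sites do not run the research procedures. These points shape the fix but do not remove the case for it.

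**Conclusion.** The concern holds as a precision and pre-specification point. The Aim 1 and Aim 2 models omit a site factor that the trial already records, and the plan does not say whether allocation was stratified by it. With 180 evaluable per arm, 50% suppression in both arms and a 13-point margin, adding clinic would gain about 0.4, 1.7 or 4.0 points of power for between-clinic SDs of 5, 10 or 15 points, and essentially nothing if clinics are alike.

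The figures rest on the assumed SDs, equal clinic sizes, missingness unrelated to clinic, and a 12-month comparison of two proportions in place of the full mixed model. In the three-visit model, one set of clinic indicators captures clinic differences only so far as they are similar across visits on the logit scale, so the realised gain may be smaller. It is still worth making the change, because the cost is low and a clinic adjustment introduced after the outcomes of an open-label trial are known could look selective.

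**What to change.** Before outcomes are analysed:

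- Define clinic as the HIV clinic to which the participant is assigned for care (and, in the BUP/NX arm, dispensing) at randomisation, fixed independently of the arm received.
- Enter clinic as a pre-specified fixed effect (five indicators) in the Aim 1 and Aim 2 models.
- Replace the inverse-logit of coefficients with a standardised RD: predict each participant's 12-month risk under both arms, average over the observed clinic mix (and over the random intercept, as a marginal risk requires), and take the delta-method standard error of that difference. The margin and decision rule are unchanged.
- State in the Randomization section whether the list was stratified by clinic.

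The allocation list should stay as it is. In a non-blinded trial with a fixed block size of 10, moving to clinic-level lists would make upcoming assignments easier for clinic staff to predict, and the documents do not say whether any enrolment remains.

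The cost is a short amendment to the analysis plan, five degrees of freedom (under 1% in SE if clinics do not differ) and a slightly more involved RD calculation. No new data are needed beyond confirming each participant's clinic at randomisation.

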Adverse Events • Paper Log • eCRF • Serious Adverse Events eCRF								X
Protocol Deviation • Paper Log • eCRF								X

Table 2: Table of Assessments								
	Pre-Screening	Screening	Baseline	3 Month	6 Month	9 Month	12 Month	As Needed Only
Study Termination Form							X	X (if ppt ends early)
*chart abstraction possible								

Visit Procedures

Survey Data

Research assistants will administer participant surveys in a confidential setting using real-time, secure, web-based electronic data entry. All survey measures have been translated into Vietnamese and been field tested and adapted for cultural appropriateness and feasibility for electronic data collection in Vietnam during previous research.

Survey data measurements include:

- Demographics
- Drug and alcohol use
- Addiction treatment
- HIV treatment
- Co-morbid conditions including physical and mental health
- Quality of life

Medical Chart Data

Research assistants will review participant HIV clinic and MMT medical charts quarterly to inform outcome measures including receipt of ART, retention in care, and adherence to study treatment condition (buprenorphine, methadone dosing, counseling visits). Medical charts will be reviewed at Baseline to establish diagnoses of Hepatitis B, Hepatitis C, and Tuberculosis. If not available in medical chart, research staff will obtain testing as necessary.

Biologic Data

Urine samples for pregnancy and urine drug screens (morphine, methamphetamine, methadone, amphetamine, buprenorphine) will be collected and processed in the HIV clinic using point of care testing.

Viral load specimens will be drawn at baseline, 6, and 12 months, and processed for transport at HIV clinic, then transported to the National Hospital for Tropical Disease for centralized lab testing. HIV viral load testing (the primary outcome) is performed with Real-time RT-PCR on Real-time ABI 7500 machine with reagents and primers made by Invitrogen.¹¹⁰ The current viral load technique is certified for a lower limit of HIV-1 RNA detection of 55 copies/mL.

All other phlebotomy measurements (Safety Labs, and CD4) will be either drawn at the appropriate times following the above schedule or will be chart-abstracted as required. They will be drawn and processed for analysis at the HIV clinic locally.

Study physicians will conduct baseline physical exams to assess for medical appropriateness for participation.

Qualitative Data

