We will conduct three sensitivity analyses. First, we will assume data are missing not at random and use single imputation of unsuppressed for missing VL data. Participants who are lost to follow-up will be imputed as treatment failures (i.e., not suppressed). Death from any cause and dropout will also be considered equivalent to non-suppression for the purposes of this analysis. Second, we will use multiple imputation with Markov-Chain Monte Carlo methods and “auxiliary variables” (i.e., covariates that are not part of the main analysis, but may help predict data missingness) to address missing data. We will include covariates associated with missingness at any time-points (using a relaxed p-value of 0.2) as auxiliary variables in our multiple imputation model. Finally, for our third sensitivity analysis, we will conduct a per-protocol analysis among participants who received at least one dose of study medication in the 90 days before each visit. If sensitivity analysis results change the primary outcome findings, we will report the results alongside our main analysis.

Secondary outcomes including binary ART initiation, ART adherence, and retention in HIV care will be analyzed using similar procedures. As these are superiority hypotheses, we will test them using two-tailed tests at an alpha level of .05.

Aim 2: Assess effect of clinic-based BUP/NX versus MMT referral on opioid use in HIV-infected participants with opioid dependence.

- **H2:** We hypothesize that participants randomized to BUP/NX will have a lower proportion of positive assessments for opioid use (self-report + UDS) at 12 months versus MMT referral

Overview. In Aim 2, we assess the effect of clinic-based BUP/NX on opioid use as measured by urine drug screens or any self-reported use in the last 30 days, assessed at 3, 6, 9, and 12 months following randomization.

Dependent variables. The primary dependent variable for Aim 2 will be the proportion of positive assessments for opioid use at 12 months, as measured by any self-reported opioid use or positive urine drug screen during the 12-month follow-up assessment (binary). We will consider secondary substance use outcomes including proportion of follow-up visits with a positive assessment for opioid use (proportion), and other illicit drug use (binary), and alcohol use (binary).

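### The auxiliary-variable rule for the multiple-imputation sensitivity analysis screens on missingness and guarantees no place to known predictors of 12-month suppression; the likely effect is small

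*Combined protocol and SAP*

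**What the plan says.** The Aim 1 Data Analysis Plan lists three sensitivity analyses. The relevant one opens "Second, we will use multiple imputation with Markov-Chain Monte Carlo methods". It describes auxiliary variables as "covariates that are not part of the main analysis, but may help predict data missingness" and then gives its selection rule: "We will include covariates associated with missingness at any time-points (using a relaxed p-value of 0.2) as auxiliary variables in our multiple imputation model". No other section adds a criterion of association with viral load or a list of variables that must enter the imputation model. The Potential Covariates paragraph lists broad domains but does not tie them to the imputation.

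Other sections bear on which variables matter:

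- Conceptual Model: "uptake of and adherence to ART (Aim 1B) are proximal outcomes that contribute to virologic suppression (Aim 1A".
- The chart-review paragraph under Visit Procedures states: "Research assistants will review participant HIV clinic and MMT medical charts quarterly to inform outcome measures including receipt of ART, retention in care". The same sentence goes on to cover dosing and counseling visits, and Table 2 schedules dosing and HIV care utilization forms at 3, 6, 9 and 12 months.
- Visit Procedures, Biologic Data: "All other phlebotomy measurements (Safety Labs, and CD4) will be either drawn at the appropriate times following the above schedule or will be chart-abstracted". Table 2 places CD4 at screening, 6 and 12 months.
- Primary model: suppression status is modeled repeatedly, with "time effect (e.g., baseline, 6, and 12 months) will be considered main effects". Baseline and 6-month suppression are therefore main-analysis variables, not auxiliary ones.

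**The concern.** An auxiliary variable does two things in an imputation model. It recovers precision to the extent that it predicts the missing value. It removes bias only if it is related both to the missing value and to the chance of being missing. A screen on missingness tests one of these two links and ignores the other. A strong predictor of suppression can fail the screen. A variable with no bearing on suppression can pass it and add only noise.

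Attrition of 20% is expected. The multiple imputation is the planned analysis best placed to bring ART and care-contact data to bear on the missing 12-month results. If those variables are not assured a place, it is a weaker check on the noninferiority conclusion than the data allow. Secondary outcomes and Aim 2 are to be analyzed in a similar way, so the rule may carry over to them.

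**Working it through.** **Inputs from the plan.** 225 per arm; 20% attrition; 50% suppression under MMT referral; margin of -13 points on the risk difference (RD), judged by the lower 95% limit; screen at p = 0.2.

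**Assumed, not in the documents.** A binary chart variable X with 70% prevalence; suppression 65% with X and 15% without it (0.7 × 0.65 + 0.3 × 0.15 = 0.50, matching the plan's rate); true RD of zero; a screen that pools the arms. The gap d is the missingness percentage without X minus that with X, with 20% missing overall.

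**The plan's own figure.** This point disputes no stated number, but the source of the 50% checks out. For 50% v 65%, two-sided 0.05, 80% power and pooled variance:

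n = [1.96 × √(2 × 0.575 × 0.425) + 0.8416 × √(0.25 + 0.2275)]² / 0.15² = (1.370 + 0.582)² / 0.0225 ≈ 169.3, so 170 per arm and 340 in total, as stated.

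**Step 1: an irrelevant variable passing.** With k independent time-points screened, the chance is 1 - 0.8^k: 20%, 36%, 49% and 59% for k = 1 to 4.

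**Step 2: a real predictor passing at one time-point.** With 315 participants having X and 135 not, the null standard error of the missingness difference is √[0.2 × 0.8 × (1/315 + 1/135)] = 0.0411. The threshold is 1.2816 × 0.0411 = 0.0527.

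| Gap, same in both arms | Kept | Left out |
|---|---|---|
| 0 points | 20% | 80% |
| 5 points | 48% | 52% |
| 10 points | 86% | 14% |
| 15 points | 98.5% | 1.5% |

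For the 5-point row, missingness is 18.5% with X and 23.5% without, and the standard error under the alternative is √(0.185 × 0.815/315 + 0.235 × 0.765/135) = 0.0425. The upper tail is Φ[(0.05 - 0.0527)/0.0425] ≈ 47.4%; the lower tail adds about 0.8%.

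**Step 3: bias if X is left out.** In an arm with gap d, the missing proportion among those with X is 0.2 - 0.3d. X is then over-represented among those observed by 0.7 × 0.3d/0.8, and suppression is overstated by 0.50 times that. For d = 0.15 this is 0.0394 × 0.50 = 1.97 points; for d = 0.10 it is 1.31 points. Equal gaps in the two arms cancel in the RD.

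**Step 4: simulation of the rule.** 4,000 trials per scenario, 20 imputations, imputed within arm, with X used always or only when it passes the pooled screen.

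| Gap, BUP/NX / MMT | X kept by rule | RD bias, rule | RD bias, always in | Coverage, rule / always |
|---|---|---|---|---|
| 0 / 0 | 21% | 0.0 | 0.0 | 95% / 95% |
| 5 / 5 | 49% | -0.1 | -0.1 | 95% / 95% |
| 15 / 0 | 69% | +0.6 | 0.0 | 94% / 95% |
| 10 / -10 | 20% | +2.2 | +0.1 | 92% / 94% |
| 15 / -15 | 19% | +3.1 | -0.1 | 90% / 95% |

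Bias is in percentage points, with simulation error about 0.0533/√4000 ≈ 0.08 point. Step 3 gives the same sizes: 1.97 × (1 - 0.69) ≈ 0.6; 2 × 1.31 × 0.80 ≈ 2.1; 2 × 1.97 × 0.81 ≈ 3.2. With no gap, the empirical standard error of the RD is 0.0525 with X always in, 0.0533 under the rule (1.5% larger) and 0.0535 with X never in (1.9% larger).

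Positive bias favors noninferiority; reversing the arms reverses the sign. The simulation leaves out baseline and 6-month suppression, which would already carry part of what X carries, so the real effect is likely smaller.

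**The case against.** The text is an inclusion rule. It does not say that other variables are barred, nor that the screen pools the arms. A reader might infer that missingness is the sole permitted criterion and that ART receipt would be thrown out. The documents do not go that far: they give no second rule, but they do not exclude one. What stands is that nothing guarantees these variables a place.

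A reader might also expect the screen routinely to lose the important variables. ART receipt, attendance and dosing all measure contact with care, and viral load specimens are drawn and processed through the HIV clinics. A person out of care is plausibly more likely to miss the draw. At a 10-point gap such a variable passes about 86% of the time, and more than one time-point gives it further chances. Frequent omission needs a small or zero gap, where there is little bias to remove, or gaps that cancel across arms. The documents give no reason to expect opposite gaps, and bias does not require them, as the one-arm case shows.

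A third tempting inference is a large gain in precision. If 70% are on ART, with suppression 75% on and 5% off (assumed), R² = 0.147²/(0.2484 × 0.21) = 0.414. The variance factor (1 - R²)/0.8 + R² is 1.147, so effective size is 225/1.147 = 196 per arm, against 225/1.25 = 180 with no predictor. That comparison ignores the 6-month result. If 6-month suppression alone explains 36% of variance and ART raises this to 45-50% (assumed), effective size moves from 225/1.16 = 194 to 225/1.1375 = 198 or 225/1.125 = 200, a gain of 4 to 6.

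Nor is this the only planned analysis to use anything beyond viral load. The first sensitivity analysis uses death and dropout, the third uses dosing, and the Aim 2 power text mentions covariate adjustment of the mixed model. Finally, chart data may be incomplete for those without a draw, and research procedures stop during incarceration. These objections limit the weight of the point. They do not supply the missing outcome criterion.

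**Conclusion.** The point holds as a minor improvement to one sensitivity analysis. The written rule does not secure strong predictors of 12-month suppression that the trial plans to collect, and it can admit variables with no link to suppression. Under the assumed predictor (70% prevalence, 65% v 15% suppression), the cost ranges from a slightly larger standard error to about 0.6 point of RD bias for a one-arm gap. The 2-3 point bias, with coverage of 90-92%, belongs to the extreme opposite-gap scenario and depends on a pooled screen, which the plan does not specify.

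A reader might conclude that the noninferiority finding itself is at risk. The documents do not support that. The primary analysis is the mixed model, and the margin and sample size do not depend on this rule.

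**What to change.** Replace the selection sentence with a pre-specified imputation model:

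- Include, whatever their p-values, baseline and 6-month viral load, CD4, and chart-abstracted ART receipt, HIV clinic attendance and BUP/NX or methadone dosing where available.
- Add other covariates associated with 12-month suppression or with missingness. Association with either is enough; a missingness-related variable should not be discarded because no outcome link was detected.
- Impute separately by arm. This puts arm in the model, lets the predictors act differently in each arm and accommodates arm-specific dosing data.
- Report, by arm, how many participants without a 12-month viral load have usable chart data.

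The cost is a few sentences in the analysis plan and slightly more analysis work, using data already planned. The benefit shrinks where charts are empty for participants without a blood draw.
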